- Expansion Group 1: Extremity STS- up to 15 locally advanced unresectable, or metastatic, intermediate, or high-grade soft-tissue sarcoma participants will be treated per study treatment in Stage 1
- Expansion Group 3a: Head & Neck- up to 13 R/M HNSCC participants will be treated per study treatment in Stage 1.

Simon 2-Stage Design Considerations

			Stage 1 responders/ Stage 1 n	Stage 2 responders/ Stage 2 n			
Cohort	Power	Historical ORR/Target ORR	Consider Futility	Go to Stage 2	Consider Futility	Consider Efficacy	Expected Sample Size
H&N	85%	20%/45%	≤3/13	≥4/13	≤8/26	≥9/26	16.28
Extremity Sarcoma	70%	20%/35%	≤3/15	≥4/15	≤13/46	≥14/46	25.91

Continuous Reassessment Method

- Expansion Group 2: Unresectable STS locally advanced or metastatic
 - Sample sizes for Expansion Group 2 participants are guided by the Continuous Reassessment Method (CRM) design ([Wheeler 2019](#)). The indicated population for the Expansion Group 2 participants is locally advanced or metastatic, unresectable, soft-tissue sarcoma of intermediate or high grade with evidence of disease progression and no prior anthracycline treatment, and thus the test statistics parameters for the CRM are based on historical toxicity and efficacy rates of said population (see below). The participants will receive SQ3370 at the RP2D administered IV as a 3-day dosing regimen per 21-day cycle or as a 5-day dosing regimen per 21-day cycle.

Continuous Reassessment Method Design Considerations

Parameters	Continuous Reassessment Method (CRM)
Historical Rates of Toxicity ²	
 • Anemia: Grade ≥ 3- [8%] • Febrile neutropenia Grade ≥ 3- [~20%]
Acceptable threshold for toxicity	Grade ≥ 3 Related Myelosuppression TEAEs* 
 • Anemia: Grade ≥ 3- <15% • Febrile neutropenia Grade ≥ 3- <15%
Maximum Inefficacy proportion ³⁻⁵	0.20
Minimum Efficacy proportion ³⁻⁵	0.35
Types I and II errors set at	0.05
Total number of pts per arm	11
Power	none

*Myelosuppression TEAEs as per NCI-CTCAE v5.0- Anemia: Grade 3: Hgb <8.0 g/dL; <4.9 mmol/L; <80 g/L; transfusion indicated. Grade 4: Life-threatening consequences; urgent intervention indicated; Febrile Neutropenia: Grade 3-ANC <1000/mm³ with a single temperature of >38.3 degrees C (101 degrees F) or a sustained temperature of >=38 degrees C (100.4 degrees F) for more than one hour. Grade 4: Life-threatening consequences; urgent intervention indicated.

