Test statistics parameters are based on historical toxicity and efficacy rates (Table 10). The acceptable threshold for toxicity is set at 15%, respectively. A toxicity rate at or above 15% for myelosuppression (Grade ≥ 3) related treatment emergent adverse events (TEAEs) (anemia and febrile neutropenia) would be considered unsafe for that cohort, and enrollment would stop. The maximum inefficacy and minimum efficacy rates are based on historical objective response rates (ORR), with <20% ORR being undesirable, and >35% ORR being desirable.

After approximately half (n=6 per arm) of participants in Group 2 have been enrolled and observed for at least 2 cycles or approximately 6-weeks and have had at least one post-baseline tumor assessment, an evaluation of all available data (safety, efficacy, and PK from both the Expansion and Dose Escalation) will be performed by the SRC, to determine whether to continue to enroll up to a total of 11 participants per arm or to stop enrollment of a cohort.

Groups 1 and 3a will treat up to approximately 28 participants in Stage 1 and Group 2 will treat up to a total of 22 participants. For all Expansion Groups: Patients may be replaced if they are enrolled into the study but do not receive (for reasons other than AEs/SAEs) the intended dose

during Cycle 1. If Cycle 1 cannot be completed due to a COVID-19 infection, an additional patient may be enrolled in the group.

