7. PLANNED ANALYSES

7.1 Interim Analysis

In Phase 2a, there will be two interim looks at the data:

- 1) run-in safety/tolerability and
- 2) Stage 1 of the Simon 2-stage design.

The SRC will utilize the same criteria to evaluate the safety and tolerability of all available safety data at the completion of timing for each group to determine the initial safety and monitor the groups throughout the study overall safety and tolerability.

Phase 2a Safety Evaluation Timing:

| Group | Run-in Evaluation N= (timing) | Simon Design: Stage 1 evaluation | Final Assessment |
|----------------------------|--|----------------------------------|------------------|
| 1: Extremity STS | N=6 (after cycle 1) | N=15 | N=46 |
| 2: STS unresectable | N=12 (6 per arm; after cycle 2) | N.A. | N=22 |
| 3a: Head and Neck | N.A. | N=13 | N=26 |

N.A.=Not Applicable

Group 3a: A run-in is not planned for the Head & Neck group (Group 3a) since they will be receiving the RP2D and schedule of SQ3370 without modifications.

Group 1: will receive SLQ70 in a volume of 20 mL with the RP2D of SQP33 and therefore the safety lead-in to this group is warranted. The SRC may, after the planned initial review of any group, within its purview recommend additional monitoring to the sponsor.

The above table also describes the Stage 1 analysis of efficacy/safety based on the Simon 2 stage design parameters.

For the Group 2 safety run-in, after approximately half (n=12 total or n=6 per arm) of patients in Expansion Group 2 have been enrolled and observed for at least 2 cycles (or approximately 6-weeks) and have had at least one post- baseline tumor assessment, an evaluation of all available data (safety, efficacy, pk) will be performed by the SRC to determine whether to continue to enroll up to Group 2 final total n=22 (n=11 per arm) or to stop enrollment.

With respect to efficacy, the minimum number of responders needed to continue to full enrollment of Group 2 will be based on the stage 1 parameters of the Simon 2-stage design. The maximum inefficacy and minimum efficacy rates are based on historical ORR and are <20% ORR being undesirable, and >35% ORR being desirable. Assuming 70% power and one-sided significance level of 0.10, with 12 Group 2 patients in the safety run-in, if ≤ 2 patients achieve either a CR or PR, then the study is considered futile and will be stopped. If ≥ 3 responders in 12 patients, then the Group 2 enrollment may continue to enroll to n=22.

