8.6 Definitions, Computations, Derived Data

- Screening: Screening is defined as ≤ 28 days prior to Cycle 1 Day 1 prior to the first study drug administration.
- Baseline: Measurements taken at Screening or prior to receiving the first dose of study drug; whichever is latest.
- Study Day and Cycle Day follows the CDISC standard and is defined as:
 - On-study Assessment Days (Assessment date – First date of study drug dosing of the first cycle) + 1, where the assessment date is on or after the first date of dosing of the first cycle.
 - Screening Days (Assessment date – First date of study drug dosing of the first cycle), where the assessment date is before the first date of dosing of the first cycle. For this protocol, screening days are from Day -28 to -1.
 - There will be no Study Day 0.
 - “Study Day x” (where $x > 0$) refers to the number of days from first dosing date in Cycle 1. For example, Study Day 1 is Cycle 1 Day 1.
- Visit Nomenclature: Nominal visits nomenclature on the CRFs and the scheduled visit will be used for summary tables.

- Scheduled visits for the Treatment Period are: "Screening", "Cycle x Day 1" (where x = 1, 2, 3, ... 9), Days 1, 2, 3, 4, 5, 10, 17, etc.
- Safety follow-up visit is 28-34 days after the last dose of study drug and on-site.
- Long Term follow-up visits are every 12 weeks (on or off site).
- Assessment for response and tumor burden is planned every 6 weeks and at Safety follow-up and long-term follow-up.
- The objective response rate (ORR): Percentage of patients whose best objective response recorded from the start of the treatment until disease progression/recurrence is a CR or PR according to RECIST 1.1 criteria.
- Best Overall Response (BOR) is defined as the best response recorded in the case report form after the start of the study treatment.
- A determination of the recommended Phase 2 dose (RP2D) will be based on the safety and tolerability from every cycle of treatment, not just Cycle 1. The RP2D will be determined based on all available data, including PK/PD analysis, tolerability that will include the incidence and severity of DLTs, other AEs and the evidence for biological activity at each dose level tested. The RP2D can be defined by an SQP33 protodrug dose and a SQL70 biopolymer volume.
- 1 year = 365.25 days. Year is calculated as (days / 365.25) and will be rounded to 1 digit after the decimal point (tenths) for presentation purposes.

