11. EFFICACY ANALYSIS

Time to event variables will be estimated using K-M methodology. Binary variables will be summarized by binomial response rates and their corresponding two- sided 95% exact CI. Categorical variables will be summarized using tables presenting counts and percentages for each category. Quantitative variables will be summarized using the mean, median, minimum, and maximum values, and standard deviation.

For the Dose Expansion portion of this study, the Treated/Full analysis set will be utilized for efficacy analyses. This analysis set consists of all patients who receive at least 1 dose of SQL70 biopolymer and 1 dose of SQP33 protodrug. The Efficacy Evaluable analysis set will also be utilized for comparison purposes. This analysis set consists of all patients who receive at least 1 dose of SQL70 biopolymer and 1 dose of SQP33 protodrug and undergo at least 1 post baseline tumor evaluation. The efficacy endpoints will be assessed by the

investigator assessed RECIST v1.1, and will be summarized in tables, listings and/or figures as outlined in the sections below.

Additional analyses may be performed to assist the Sponsor in planning future studies.

In addition to the summary tables, efficacy data will also be presented in the individual patient listings.

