11.1 Objective Response Rate (Groups 1, 2, and 3a)

Objective response rate (ORR) is defined as the number and percentage of participants with a best overall response (BOR) of confirmed CR or PR. BOR is defined as the best response designation, recorded between the date of enrollment and the date of the initial objectively documented tumor progression per RECIST v1.1, date of death from any cause, or the date of subsequent therapy, whichever occurs first. For participants without documented progression or subsequent therapy, all available response designations will contribute to the BOR determination.

The overall response rate (ORR) will be summarized with the number and percentage of patients along with the corresponding two- sided 95% exact confidence interval (CI). by Phase 2a expansion group. In addition, a swimmer's plot will be constructed. This will depict time on study, CR/PR date, disease progression (and/or death) date, end of treatment/study date, etc. This swimmers plot will also help visualize the other efficacy endpoints using RECIST1.1 described below (i.e., duration of response, disease control rate, and disease control rate).

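### The 70% power and one-sided 0.10 alpha stated for the Group 2 look at 12 patients cannot be reached with 22, and the CRM table's 0.05 type II error contradicts its own power entry of none

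*SAP*

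**What the plan says.** Phase 2a SAP section 7.1 bases the Group 2 efficacy look on stage 1 of a Simon two-stage design. The rates are "<20% ORR being undesirable, and >35% ORR being desirable", and the design inputs are given as "Assuming 70% power and one-sided significance level of 0.10, with 12 Group 2 patients in the safety run-in". With 2 or fewer responders the group is futile and stops. Otherwise: "If ≥ 3 responders in 12 patients, then the Group 2 enrollment may continue to enroll to n=22". No success cut-off at 22 is stated, and the timing table in the same section marks the Simon stage 1 evaluation as not applicable to Group 2.

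The CRM table for the same group appears in the Protocol synopsis, in Protocol section 8.3 (Table 10) and in SAP section 4. Its row "Types I and II errors set at" has the value 0.05, the sample size is 11 per arm, and the power row reads none.

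The response definition varies. SAP 7.1 counts CR or PR. SAP 8.6 defines ORR as "Percentage of patients whose best objective response recorded from the start of the treatment until disease progression/recurrence is a CR or PR". SAP 11.1 defines it as the "number and percentage of participants with a best overall response (BOR) of confirmed CR or PR". Under Protocol 8.3 the look takes place once patients have been followed for about 6 weeks and "have had at least one post-baseline tumor assessment".

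**The concern.** Alpha and power describe a finished test with a final decision rule. Here they are attached to a first-stage cut-off followed by a sample size with no decision rule, and 22 patients looked too few for 20% against 35% at those error rates. The plan's own Group 1 design, with the same rates and about the same power, takes 46 patients, although at alpha 0.0498.

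In the CRM table, a type II error of 0.05 is by definition 95% power, so it cannot sit beside a power entry of none.

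The look can close Group 2. The Safety Review Committee and later readers could credit it, and the 22-patient result, with error control that the design lacks. Because the response that counts is not fixed, the same 12 patients could mean stop under one SAP definition and continue under the other.

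**Working it through.** **Inputs.** p0 = 0.20, p1 = 0.35, stop at 2 or fewer of 12, total 22 (SAP 7.1); 11 per arm, errors 0.05, historical toxicity 8% and about 20%, acceptability threshold 15% (CRM table).

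**Formula.** With stage 1 size n1, stop at r1 or fewer, total n, and success at c or more responders:

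P(success | p) = Σ over x > r1 of P(Bin(n1, p) = x) × P(Bin(n − n1, p) ≥ c − x).

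Alpha is this value at p0 and power is its value at p1.

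**Check on the plan's other designs.** Group 1 (3/15, 13/46) gives alpha 0.0498, power 0.705 and early termination 0.648, as stated. Group 3a (3/13, 8/26; 20% against 45%) gives 0.0498 (stated as 0.049), 0.851 and 0.747. The method therefore matches the one used for those groups.

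**The Group 2 look alone.**
- At 20%: P(X ≤ 2 of 12) = 0.0687 + 0.2062 + 0.2835 = 0.558, so it continues with probability 0.442.
- At 35%: 0.0057 + 0.0368 + 0.1088 = 0.151, so it continues with probability 0.849.

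**The look followed by 22 patients.**

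| Success at 22 | Alpha | Power |
|---|---|---|
| 6 or more | 0.226 | 0.775 |
| 7 or more | 0.122 | 0.667 |
| 8 or more | 0.054 | 0.515 |
| SAP 7.1 states | 0.10 | 0.70 |

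No row meets both stated figures. Among all two-stage designs with n ≤ 22 and alpha ≤ 0.10, the highest power is 0.612 (stop at 3/14, reject the drug at 6/21 or fewer; alpha 0.099). With the 2/12 look fixed, the first total that meets 0.10 and 0.70 is 33 (success at 10 or more: 0.091, 0.708).

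**The CRM row.** The table does not say which comparison the 0.05 refers to, so both readings were tried for one arm of 11. The toxicity hypotheses are constructed from the table's rates; the plan does not define them as null and alternative.
- Response, 20% against 35%: 5 or more gives 0.0504 and 0.33; 6 or more gives 0.012 and 0.15. An exact single-stage test with both errors at 0.05 needs 98 patients (27 or more: 0.0446, 0.953).
- Anemia, 8% against 15%: 3 or more events gives 0.052 and 0.22; 4 or more gives 0.009 and 0.07. Both errors at 0.05 need 220 patients.
- Febrile neutropenia, showing a rate below 20%: even 0 of 11 has probability 0.8^11 = 0.086, above 0.05.

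**Late or unconfirmed responses (illustration; the fractions are assumptions, not from the documents).** If only a fraction f of responders has a countable response at the look, the stopping probability at a true 35% is P(Bin(12, 0.35f) ≤ 2): 15% for f = 1, 22% for 0.9, 41% for 0.7, 65% for 0.5. Scans are every 6 weeks (Protocol 6.18), so a patient seen at the minimum follow-up may have only one post-baseline scan and no opportunity for confirmation.

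**The case against.** The strongest reply is that 70% and 0.10 were only inputs used to choose the first-stage cut-off, and that the SAP never claims a test at 22. ORR is a secondary endpoint, and SAP section 11 plans only estimation: "Binary variables will be summarized by binomial response rates", with exact 95% intervals. It is true that 2/12 is a legitimate first stage for those inputs. But it belongs to a design of at least 33 patients, and the text attaches it to 22 without saying so, so the stated properties remain ones this plan does not have.

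Several narrower points stand. The CRM row conflicts with SAP 7.1 only if its 0.05 refers to response; the conflict inside the table holds either way. The febrile neutropenia result applies to one arm of 11: pooled over both arms, 1 or fewer of 22 has probability 0.048 at 20%. The differing response definitions apply to all groups, though they matter most where a small count decides stopping. Correcting the headline figures changes no Group 2 decision, since the cut-off stays. The Phase 2a SAP is marked version 0.1, so it can still be corrected, but that does not make the figures right.

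**Conclusion.** Wrong as written. The 12-then-22 plan cannot have one-sided alpha 0.10 together with 70% power; the nearest options are 0.122 with 66.7% and 0.054 with 51.5%. This rests on exact binomial calculation with the two arms pooled, as the rule itself pools them, and on the SAP's own rates of 20% and 35%. The CRM table contradicts itself whatever its 0.05 refers to, and 11 patients per arm cannot deliver that error rate on either reading tried. The undefined response at the look is a secondary point but the only one that could change a decision; its size depends on how many responses are countable by then, which the documents do not give. The look itself is sound enough to keep. This should be fixed, but it does not undermine the group's primary safety purpose.

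**What to change.** - **SAP 7.1:** replace the power and alpha clause with the look's actual properties: it continues with probability 44% at a response rate of 20% and 85% at 35%. Add that the final Group 2 response rate is descriptive with an exact 95% interval; 7/22, for example, gives 14% to 55%. If a test at 22 is wanted, name the cut-off with its error rates: 7 or more (alpha 12.2%, power 66.7%) or 8 or more (5.4%, 51.5%).
- **CRM table:** delete the 0.05 error row in the Protocol synopsis, Protocol Table 10 and SAP section 4.
- **Response at the look:** state in SAP 7.1 which response counts, for example unconfirmed CR or PR at the time of the look, and note that the 85% holds only if all responders have declared by then.
- **SAP section 16:** record the 2/12 rule, which the Protocol does not contain although the section lists no changes.

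The cost is text: one SAP sentence, one table row in three places, one definition and one log entry. No patients are added and the look is not delayed. Two of the three row deletions are in the Protocol and must follow its amendment process (section 11.2). Until then, the SAP correction can carry the point, since the SAP says it supersedes the Protocol's statistical considerations. The stated properties become less favourable.

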7.2 Final Analysis

The final tables, listings, graphs, and data analysis will be conducted once all study participants have completed the phase 2a of this study and the clinical database has been locked.

8. DATA PRESENTATION AND HANDLING

8.1 Table and Individual Patient Data Listing Considerations

Summary tables and listings will be prepared according to ICH Guideline E3 (as appropriate for a Phase 2A study).

In general, summary tables will be organized with respect to the Phase 2A expansion groups:

- Group 1: Extremity STS
- Group 2: Unresectable STS 3-Day Infusion
- Group 2: Unresectable STS 5-Day Infusion
- Group 3A: Head and Neck
- Total

Row entries in post text tables are made only if data exists for at least one patient (e.g., a row with all zeros will not appear). The only exception to this rule will apply to tables that summarize the study termination status of patients (e.g., reasons for not completing the study). In this case, zeros will appear for study termination reasons that no patient satisfied. The summary tables will clearly indicate the number of patients to which the data apply and unknown or not performed are distinguished from missing data.

Summary tables for any concomitant medications will be coded according to the World Health Organization (WHO) Drug dictionary September 2020 (or later). Adverse event preferred terms and body/organ systems and medical history conditions will be coded using the Medical Dictionary for Regulatory Activities (MedDRA®) dictionary Version 24.1 (or later).

Listings will also be sorted by expansion group (where applicable) and patient number. Listings will also include visit number, visit date/time and days relative to the initiation of study treatment.

In general, missing data will not be imputed unless otherwise specified. Any imputed or derived data will be flagged in the individual patient data listings. Imputed data will not be incorporated into any raw or primary datasets. These data will be retained in derived analysis datasets.

8.2 Format Considerations

The tables, figures and listings will be numbered using a decimal system to reflect main levels of unique tables and listings and sub-levels of replicate tables and listings with two digits per level (e.g., Table XX.YY.ZZ.).

1. The first level number will be consistent with the corresponding Clinical Study Report (CSR) appendix in which the tables or listings will appear. For example, the post text tables will appear in Appendix 14 (and will be numbered 14.XX.YY) and the individual patient data listings will appear in Appendix 16 (and will be numbered 16.XX.YY). The patient disposition table will be first in the first section of the report and will be numbered Table 14.1. The supportive patient data listing will be Listing 16.1. Any subset table will have the number Table 14.1.2, etc.
2. Table numbering will follow ICH E3 for Phase I CSRs. Patient disposition, baseline and demography and prior and concomitant medications tables should appear as the second level number (Table 14.1 series). Efficacy tables will occupy the next sub-level (Table 14.2 series – 14.2.1, 14.2.2 and 14.2.3, respectively). Safety tables will follow next (Table 14.3 series). Similar conventions will be applied to the patient data listings.
3. Each table and listing title will be complete, accurate and concise. The last line of the title will provide the analysis group being summarized (e.g., Safety Population or Efficacy Evaluable Population).
4. If possible, variables being summarized, and statistics reported will appear in the left most column of a table. The next columns for dose expansion groups should report the data from left to right per group number (1, 2, 3A). .

8.3 Data Management

All data will be recorded by the site in individual source documents. An eCRF will be created by the data management vendor (Novotech) for recording of the required data in the study database. All eCRF information is to be filled in by site staff. If an item is not available or is not applicable, this fact should be indicated. Blank spaces should not be present unless otherwise directed.

The study monitor will perform source data verification of data entered into the eCRF and raise queries for correction by the site. The data entered into the eCRF will be patient to data validation checks for consistency and completeness by the data management vendor

and sponsor. Data queries will then be generated and sent to the investigational site for response before the database is locked and released for statistical analysis.

Database building, AE coding, medication coding, data cleaning will be conducted according to the Novotech (vendor clinical research organization) Data Management Plan for this specific study.

Derived datasets (including SDTM and ADaM) will be created using SAS® software. Data analyses and summary tables will be generated using the currently supported version at the time of data analysis (currently version 9.4).

